- Determine whether exposure to Pf erythrocytic stage antigens between 0 to 5 months of age, or between 5 to 10 months of age, affects the type and quality of immune responses.
- 2) Evaluate the role of oxidative stress measured as the antioxidant / pro-oxidant balance in the development of NAI in children exposed to Pf erythrocytic stage antigens between 0 to 5 months of age, or between 5 to 10 months of age, compared to infants with continuous exposure.
- 3) To study the host genetic factors that influence the development of NAI to malaria in early life.

(Amended 10 August, 2005)

POTENTIAL IMPLICATION OF THE RESEARCH

The most important implication of this work is with regard to vaccine administration or administration of other strategies to prevent malaria and the design of trials. If our results indicate that exposure prior to 5 months of age does not contribute to the development of protective immune responses against *P. falciparum*, it will be necessary to address the optimal time during infancy for immunizing with a vaccine designed to induce such protective immune responses. In many areas of sub-Saharan Africa, malaria immunization alongside the EPI schedule (i.e. 6, 10, and 14 weeks) has been viewed as the most desirable approach because of issues of compliance and funding, and in order to generate protective immune responses prior to 6 months of age, when morbidity and mortality drastically increase. The studies proposed here should provide critical information regarding whether vaccination according to the EPI schedule or implementation of of other malaria-control strategies could be expected to result in adequate induction of protective immunity in infants and children or whether immunization or implementation later in infancy may be more appropriate.

HOW THE PROPOSED STUDY DESIGN ADDRESSES THE AIMS

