If the pregnant woman/mother is HIV-positive she will not be invited to participate in the study, and will be followed up at the Day Hospital following standard procedures, according to national guidelines, which includes HAART (see above for details). The investigators will not have access to any of the VCT center records and will receive no information at all on the HIV-status of women who are not enrolled in the study.

(Amended 15 October, 2004) (Amended 2 December, 2004) (Amended 11 July, 2005) (Amended 10 August, 2005)

iii. Experimental Cohorts

Infants who meet the criteria to participate in the study will be assigned to one of the 3 cohorts by block randomization, in order to adjust for seasonality of malaria infection. Thus, for every 6 infants, 2 will be randomized to each of the 3 cohorts. Enrollment of infants will continue over a one year period. Cohort 1 will receive chemoprophylaxis with SP+AS from 2 to 5 2,5 to 5,5 months of age (doses at months 2, 3 & 4 2,5; 3,5; 4,5) and placebo from 5 to 10 5,5 to 10,5 months of age. Cohort 2 will receive placebo from 2 to 5 2,5 to 5,5 months of age and chemoprophylaxis from 5-10 5,5 to 10,5 months of age (doses at months 5, 6, 7, 8 & 9 5,5; 6,5; 7,5; 8,5; 9,5), and Cohort 3 will receive placebo from 2 to 10 2,5 to 10,5 months of age. Placebo tablets will look exactly the same as the SP and AS tablets, with the same shape, size and colour. The treatment or placebo will be packed in individually numbered envelopes/bags. Doses of SP+AS/placebo will be administered on a monthly basis by a health assistant according to bodyweight (SP: single dose of 25 mg/kg Sulphadoxine and 1.25 mg/kg Pyrimethamine; AS: 4 mg/kg/day for three days). Tablets will be crushed and mixed with water on a tablespoon and administration will be directly observed. Infants will be observed for 30 minutes and a repeat dose will be given if vomiting occurs within that time. Infants from all three cohorts will be invited to the health post on month 2, 3, 4 and 9 to receive the EPI vaccines and the investigators will make sure they receive them. Subjects will be followed by active case detection as well as passive case detection until 10.5 months of age and by passive case detection and montly home visits from 10,5 to 25 24 months of age (see section v). (Amended 2 December, 2004) (Amended 11 July, 2005)

Rationale for the 3 cohorts:

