Our prediction: We hypothesize that the level of antibodies will be statistically significantly lower in Cohort 2 as compared to either Cohort 1 or Cohort 3 at the 10 month old cross-samplings and that this reduction will correlate with an increased relative risk of one or more clinical episodes of malaria in the second year of life.

Proposed analysis: Immunological endpoints will be based upon levels of antibodies (intensity) and the ratio of Th1/Th2 cytokines at each of the cross-sectional time points. For the first analysis, values for antibodies and cytokine ratios for each cohort will be compared at each cross-sectional timepoint. For the second analysis, values for antibodies and cytokine ratios at each of the timepoints will be correlated with risk of clinical outcome(s) for each cohort and between cohorts. Immunological data will be analyzed in two different ways:

- **Cross-sectionally** the key analysis will be comparison of immunological markers between cohorts, not individuals, to show differences in the development of acquired immunity to malaria attributable to age of first exposure to Pf antigens. The key timepoint for comparison is considered to be 10 months. We will explore the profile of immune responses and how markers change with age. Specifically, we predict the following outcomes:

X1; t= 2,5 month 0 or enrollment. No difference between the 3 cohorts

X2, t=5 5,5 month: No difference between the 3 cohorts

X3, t=10 10,5 month (*key comparison*): Cohort 2 will have significantly lower levels of anti-PfEMP-1 antibodies and/or Th1/Th2 cytokine ratios than cohort 1 and 3. Cohort 1 = cohort 3. **X4**, t=12 month: same as X3.

X5- **X4**, t=15 month: same as X3.

X6, t= 20 month: No difference between the 3 cohorts.

X7- **X5**, t= 25 **24** month: same as X6. We expect the immune responses to equalize between cohorts by 20-25 months.

(Amended 2 December, 2004) (Amended 11 July, 2005)

- **Prospectively**: To look for correlates of immune responses and clinical outcome. Specifically, acquisition of immune response at the level of the individual subject (as opposed to cohort) in cohort 1 vs. 2, and correlation with how that individual responds to infection and the relative risk of clinical disease. We will evaluate whether lack of exposure at different ages (0-5 months, or 5-10 months) during first 2 years of life results in differences of antibody and/or cytokine markers between the different cohorts.

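### The 5.5-month immune survey is set up as three cohorts with a predicted null and no margin, although only two treatment conditions exist by then; one contrast, Cohort 1 against Cohorts 2 and 3 combined, with an interval, would be more precise

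*Protocol*

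**What the plan says.** Secondary aim 1 (Protocol, section C), which concerns immune responses, opens "Determine whether exposure to Pf erythrocytic stage antigens between 0 to 5 months of age, or between 5 to 10 months of age, affects the". Section D.xi.2.a sets the analysis: "For the first analysis, values for antibodies and cytokine ratios for each cohort will be compared at each cross-sectional timepoint". It adds that "the key analysis will be comparison of immunological markers between cohorts, not individuals". Among the predicted outcomes it lists "X2, t=5 5,5 month: No difference between the 3 cohorts" (the amended text prints the old and the new age side by side). The same section states that "The key timepoint for comparison is considered to be 10 months", and marks the next survey, at 10.5 months, as the key comparison.

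The regimens are in section D.iii: "Cohort 2 will receive placebo from 2 to 5 2,5 to 5,5 months of age" and "Cohort 3 will receive placebo from 2 to 10 2,5 to 10,5 months of age". Cohort 2's first active dose falls due at 5.5 months, the age of the survey. No text combines the two placebo cohorts at X2, and no margin or interval accompanies the prediction.

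**The concern.** X2 is taken at the end of the early window, before the later regimens separate the cohorts, so it bears directly on the early-exposure half of secondary aim 1. Two features weaken it. First, allocation is random and Cohorts 2 and 3 are treated alike until 5.5 months, so a difference between them at X2 can only be chance, while dividing the placebo infants makes the useful comparison less precise. Second, any response occurs only in infants who were infected. If few were, the cohort mean barely moves, however well those few responded. A prediction of no difference, with no margin, is then met by imprecision alone, and the reader cannot tell absence of response from absence of infection.

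**Working it through.** **The plan's own figure.** The protocol gives no power for X2. Its sample size is for the clinical outcome (section D.ix): 78 per cohort, 98 after 20% loss. Two Poisson rates of 0.4 and 0.8 per person-year at two-sided 0.017 and 80% power give n = (2.387 + 0.842)² × (0.4 + 0.8) / (0.8 − 0.4)² = 78.2, and 78 / 0.80 = 97.5, so 98. This reproduces. The last amendment raises the total to 350, about 117 per cohort. I use n = 98 as the central case and n = 117 as the upper one.

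**Share of placebo infants exposed.** The Manhiça incidence table (section D.i) gives 35 episodes in 9491 person-weeks at 2 to under 6 months, or 0.369 per 100 person-weeks. From 2.5 to 5.5 months is 13.04 weeks.
- Clinical episodes only: 1 − exp(−0.00369 × 13.04) = 4.7% (3.8% to 6.3% over the printed interval of 0.3 to 0.5).
- Five-fold allowance for subclinical infection (assumed): 21% by the same formula, 24% by simple multiplication.
- Sensitivity, from children aged 12 to 18 months at the former site (section D.i): parasitaemia 3.3 and clinical episodes 0.48 per child-year, ratio 6.9. Applied to the rate above, this gives about 28%. Using 3.3 per child-year directly over a quarter-year gives 1 − exp(−0.825) = 56%.

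**Shift in the cohort mean.** Shift = share exposed × response in exposed infants. The protocol gives no SD or response size, so I assume 1 SD. The shift is then about 0.05 SD on clinical episodes only and up to 0.24 SD on the five-fold allowance.

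**Precision.** In SD units the standard error is √(1/n + 1/n) for one cohort against one, and √(1/n + 1/(2n)) for one against two. The ratio is √(1.5/2) = 0.866, or 13% smaller.

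**Power**, two-sided 0.05, noncentral t:

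| True difference (SD) | n = 98: 1 vs one placebo cohort | n = 98: 1 vs 2+3 | n = 117: 1 vs one placebo cohort | n = 117: 1 vs 2+3 |
|---|---|---|---|---|
| 0.05 | 6.4% | 6.9% | 6.7% | 7.3% |
| 0.24 | 39% | 49% | 45% | 56% |
| 0.35 | 68% | 80% | 76% | 87% |
| 0.56 | 97% | 99% | 99% | >99% |

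At 4.7% exposed, even a 3-SD response moves the mean by only 0.14 SD, with about 17% power pairwise at n = 98.

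**Interval width.** At n = 98 the 95% half-width is 1.96 × 0.143 = 0.28 SD for the pairwise contrast and 1.96 × 0.124 = 0.24 SD for the combined one.

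**The case against.** - **A null at X2 is not given evidential weight.** A reader might infer that a non-significant X2 would be counted as confirming the central hypothesis. The protocol does not say so. X2 is one line in a list of predictions, the criterion for support in section D.xi.1.b is the clinical relative risk in Cohort 2, and the key immune comparison is at 10.5 months. This stands, and it lowers the importance of the point.
- **A null is not assured.** A reader might also infer that X2 could hardly come out otherwise. That holds only if exposure is close to clinical incidence. Power is 39% to 45% at 0.24 SD and above 95% at the former site's parasitaemia rate. Those rates come from older children at a site since replaced, so they do not settle the matter, but they show that the share exposed is unknown. This stands.
- **Combining does not cure dilution.** Correct: at 0.05 SD the gain is half a percentage point. Combining helps at intermediate exposure; at low exposure only the interval and a cautious reading help.
- **The contrasts may be set elsewhere.** Section D.xi.2.c plans an analysis of variance with planned contrasts for plasma cytokines but does not list them. Nothing in the protocol rules out the combined contrast. Its text nonetheless frames X2 as three cohorts, and that framing is what needs changing.
- **Exposed infants are studied directly.** Acute and convalescent samples and individual-level analyses are planned. This limits the harm only partly. Convalescent samples follow the first clinical episode, about 4 to 6 infants per placebo cohort by 5.5 months (4.7% of 78 to 117). Weekly visits take blood only with fever or a history of fever, and parasitaemia at the 5.5-month survey is determined only in febrile children (sections D.iv and D.vi), so subclinical exposure in this window goes largely unmeasured.

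**Conclusion.** The point holds in limited form. At X2 there are two treatment conditions, the plan compares three groups, and it predicts no difference without a margin. The combined contrast reduces the standard error by 13% at no cost, worth about 10 to 12 points of power at n = 98 for differences of 0.24 to 0.35 SD, and almost nothing at 0.05 SD. Whether a cohort-level null is expected despite a real response depends on the share exposed: yes if it is near 5% and the response is 1 SD; less so as subclinical infection rises. The response size and the five-fold allowance are assumptions. Combining also assumes that the 5.5-month sample precedes any effect of Cohort 2's first active dose. Since X2 is a secondary, non-key timepoint, this is a minor improvement.

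**What to change.** In section D.xi.2.a, replace the three-cohort comparison at X2 with one contrast, Cohort 1 against Cohorts 2 and 3 combined, using samples drawn before Cohort 2's 5.5-month active dose, and report the difference with its 95% confidence interval. Replace the X2 prediction with a statement that a non-significant result is not evidence that early exposure produces no response, and that the conclusion extends only to effects the interval excludes. The cost is analysis wording, with no extra samples or visits. The stated prediction becomes weaker.

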(Amended 11 July, 2005) (Amended 10 August, 2005)

viii. Outcome Variables

1. Clinical outcome variables

a) Primary clinical outcome variable

The experience of having at least one episode of clinical malaria in the second year of life *detected by passive case detection.* (Amended 2 December, 2004)

b) Secondary clinical outcome variables

1. Fever (axillary temperature \geq 37.5° C or a history of fever in the previous 24 hours)

2. Hct during first, second and subsequent malaria infections, and during the **24 months** cross-sectional surveys.

3. Density of parasitemia during first, second and subsequent malaria infections, and during the **24** *months* cross-sectional surveys.

4. Time to first clinical episode during the second year of life *detected by passive case detection*.

5. Number of clinical episodes during the first year of life *detected by active or passive case detection*.

6. Number of clinical episodes during the second year of life *detected by passive case detection*. (Amended 2 December, 2004)

2. Immunological outcome variables

a) Primary immunological outcome variables:

 Anti-*Pt*EMP1 antibodies in peripheral blood, as measured at 0, 5, 10, 12, 15, 20 and 25 2.5, 5.5,
10.5, 15 and 24 months of age. The outcome variable to be compared between the cohorts will be: -Antibody units converted from median fluorescence intensity [31]

2. Level-Magnitude and frequency of cytokines (IFN- γ , IL-10) in peripheral blood in response to *in vitro* stimulation with Pf parasite antigens, as measured at 0, 5, 10, 12, 15, 20 and 25 2.5, 5.5, 10.5, 15 and 24 months of age

3. Ratio of Th1 (IFN- γ , TNF α , IL-12 and IL-2) to Th2 (IL-10, IL-5, IL-4) cytokines in plasma, as measured at 0, 5, 10, 12, 15, 20 and 25 **2.5, 5.5, 10.5, 15 and 24** months of age.

4. Anti-GPI antibodies in peripheral blood as measured at 2.5, 5.5, 10.5, 15 and 24 months of age. The outcome variables to be compared between the cohorts will be: -Antibody units converted from ELISA titre -Antibody units converted from Functional Neutralization Assay.

Final protocol: 2nd July 2004 Amendment 1: 15th October 2004 Amendment 2: 2nd December 2004 Amendment 3: 11th July 2005 Amendment 4: 10th August 2005 Amendment 5: 12th September 2006 CONFIDENTIAL

Page 24 of 51

CSI/CISM

5. Host genetics:

-Presence of homozygote or heterozygote for each particular SNP. -Presence or absence of nominated haplotype for each gene.

(Amended 11 July, 2005) (Amended 10 August, 2005)

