future. It requires very small quantities of sample (5-50 μ l), making it very useful for studies in infants. This method generates data comparable to ELISA based assays but in a "multiplexed" fashion, and with more sensitivity (9-15 pg/ml for these cytokines) and reproducibility [76]. Concentration of unknown cytokines is calculated for the CBA as with any sandwich format assay, i.e. through the use of known standards and plotting unknowns against a standard curve, and results can be easily analyzed by linear regression. Forward vs. side scatter gating is employed to exclude any sample particles other than the polystyrene beads (7.5 μ m). Data is displayed as two-color dot plots (FL-2 vs. FL-3) such that the six discrete FL-3 microparticle die intensities are distributed along the Y-axis. A wide variety of preset configurations enable the user to set up standard dilution series, generate calibration curves with either 4-parameter logistic or log-log curve fit models, and subsequently compare unknowns. The data output from a CBA is not restricted to numbers from a curve: the BDA dot plot display generated via a flow cytometer creates unique profiles or signatures for each cytokine that provide with additional information at a glance.

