-Antibody units converted from ELISA titre (titer log₂(titer/10)+1 with reference to last dilution causing positive ELISA as compared with non-specific background and the ratio of IgM, IgG1, IgG2, IgG3 + IgG4 isotypes as measured in the same way)

-Antibody units converted from Functional Neutralization Assay.

(Amended 11 July, 2005)

c) Analysis and interpretation of cellular immunoassays

- The **cytokine intracellular staining** of whole blood will provide information about Pf antigen specific expression of IFN- γ and IL-10 in peripheral blood, the phenotype of the lymphocyte population expressing each cytokine (produced by CD4 or CD8 T cells), as well as the status of activation (CD69 marker) of the cells. Data will be acquired by flow cytometry and analyzed using the CellQuestTM software. Results will be expressed as frequency (%) of cytokine positive CD4+ or CD8+ T cells, and mean fluorescence intensity. For statistical analysis, data on the mean frequency of cytokine expression will be compared between cohorts by t-test or regression analysis; p<0.05 will be considered statistically significant.

- The concentration of unknown cytokines (IFN- γ , IL-10, TNF- α , IL-5, IL-4 and IL-2 and IL-12) in plasma is calculated in the Cytometric Bead Array (CBA) or equivalent via extrapolation from a curve of known standards. Standard curves are plotted [cytokine calibrator concentration vs. FL-2 mean fluorescence intensity] using a 4-parameter logistic curve fitting model. Cytokine concentrations (pg/ml) are determined from these standard curves. If the plasma has a cytokine concentration below the detection limit for the assay, a value of 0 will be assigned. All data will be presented as mean \pm standard error. In addition, cytokine ratios will be calculated to determine the Th1 vs. Th2 balance of cytokines.

Final protocol: 2nd July 2004 Amendment 1: 15th October 2004 Amendment 2: 2nd December 2004 Amendment 3: 11th July 2005 Amendment 4: 10th August 2005 Amendment 5: 12th September 2006 CONFIDENTIAL

Page 35 of 51

Results will be analyzed using the manufacturer's software. Data will be analyzed by a general linear model analysis of variance (ANOVA) with pre-planned comparisons to generate two-tailored p-values. Fisher least significant-difference tests will be used to make appropriate post ANOVA comparisons.

d) Analysis and interpretation of immunogenetic data

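### Setting undetectable plasma cytokines to 0 makes the Th1/Th2 ratio, a primary immunological outcome, infinite or undefined whenever the Th2 part is undetectable

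*Protocol*

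**What the plan says.** Section D.xi.2.c of the protocol (analysis of cellular immunoassays) fixes the handling of non-detects: "If the plasma has a cytokine concentration below the detection limit for the assay, a value of 0 will be assigned". It then asks for means with standard errors and continues: "In addition, cytokine ratios will be calculated to determine the Th1 vs. Th2 balance of cytokines". The method is given as "Data will be analyzed by a general linear model analysis of variance (ANOVA) with pre-planned comparisons", followed by Fisher least-significant-difference tests.

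Section D.viii.2.a, under the heading "a) Primary immunological outcome variables", lists as item 3 the ratio of the Th1 cytokines (IFN-γ, TNFα, IL-12 and IL-2) "to Th2 (IL-10, IL-5, IL-4) cytokines in plasma". It does not say whether the cytokines within each group are summed, averaged or paired.

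Section D.xi.2.a gives the ratio its role in the analysis: "Immunological endpoints will be based upon levels of antibodies (intensity) and the ratio of Th1/Th2 cytokines at each of the cross-sectional time points". It names about 10 months (10.5 in the amended schedule) as the key comparison, predicts lower antibodies and/or lower ratios in Cohort 2, and plans to relate the ratios to clinical risk.

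On the assay, section D.x.3 describes a six-cytokine bead array "with more sensitivity (9-15 pg/ml for these cytokines) and reproducibility", and allows an equivalent kit.

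**The concern.** A ratio needs a denominator above zero, and the stated rule creates zeros. The mean, the standard error and the ANOVA all need finite values, and the protocol has no provision for a zero denominator: no positive substitute, exclusion, transformation or rank method. An analyst who follows the text literally cannot complete the analysis of a listed primary immunological outcome and has to improvise, possibly after seeing the data.

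The obvious improvisation is to drop the samples that do not compute. Those are the samples with the lowest Th2 values, so the exclusion would depend on the outcome being compared.

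The protocol does give a rule for a comparable quantity. In section D.xi.2.b the cytophilic to non-cytophilic IgG ratio is limited to plasma with detectable IgG. Nothing similar is stated for cytokines.

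**Working it through.** The protocol gives no power figure for the cytokine ratio and no expected share of non-detects, so there is no stated figure to reproduce. The check is algebra, followed by a range over an assumed share.

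**Algebra under the zero rule**
- Th1 > 0, Th2 = 0: the ratio is infinite.
- Th1 = 0, Th2 = 0: the ratio is undefined.
- Th1 = 0, Th2 > 0: the ratio is 0, which is defined.

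One infinite value is enough to break a cohort: the values 1, 2, 0.5 and infinity have an infinite mean and a standard deviation that cannot be computed.

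**Inputs**
- Share q of samples that are non-detects for each Th2 cytokine: 0.2, 0.4 and 0.6 (assumed).
- Three Th2 cytokines: IL-10, IL-5 and IL-4 (section D.viii.2.a).
- Infants per cohort: total 350, three cohorts, 20% loss (section D.ix), so 350/3 × 0.8 ≈ 93. The 20% is the loss over the whole two years, so somewhat more infants would be present at 10.5 months.

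**Formulas**
- Ratio of sums, independent non-detects: P(denominator = 0) = q³.
- Ratio of sums, fully concordant non-detects: P = q.
- Single-cytokine ratio: P = q.
- Chance that a cohort of 93 has at least one failed ratio of sums (independent): 1 − (1 − q³)^93.

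| q (assumed) | Sums, independent | Infants of 93 | Chance of at least one | Sums concordant, or single-cytokine | Infants of 93 |
|---|---|---|---|---|---|
| 0.2 | 0.2³ = 0.8% | 0.7 | 53% | 20% | 18.6 |
| 0.4 | 0.4³ = 6.4% | 6.0 | over 99% | 40% | 37.2 |
| 0.6 | 0.6³ = 21.6% | 20.1 | about 100% | 60% | 55.8 |

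**Simulation of a replacement rule**

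Lognormal cytokines were drawn with log-SD 1 and an assumed limit of 12 pg/ml, inside the protocol's 9–15 pg/ml, with 20,000 samples per scenario.

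| Share of non-detects | Non-finite, zero rule, sums | Non-finite, zero rule, single-cytokine | Non-finite, limit/2 on the log scale, sums |
|---|---|---|---|
| 24% | 1.5% | 25% | 0 |
| 50% | 12.7% | 50% | 0 |
| 76% | 43.3% | 76% | 0 |

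With limit/2, a sample in which every cytokine is undetectable still takes a fixed value. For a common limit L and summed cytokines it is (4 × L/2)/(3 × L/2) = 4/3, whatever the true concentrations.

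**The case against.** The strongest reply concerns size and direction. Grouping the cytokines is the more natural reading of the outcome. If non-detects are then few and independent, the ratio fails in about 1% of infants. That stands as one end of the range. It does not remove the defect, because the combination is not stated, concordant non-detects would make a summed ratio fail as often as a single-cytokine one, and a single infinite value stops the stated analysis.

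Three stronger readings are tempting, and the protocol supports none of them.

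- A reader might infer that the failures fall on the infants of most interest, or mostly on the less exposed cohort. No non-detect rate is given by cohort or age. The rule applies to total plasma cytokines, which section D.x.3 distinguishes from antigen-specific responses. The predicted lower ratio in Cohort 2 could arise from a lower numerator, which gives a defined 0.
- A reader might infer that the planned analysis is already biased by exclusion. The protocol nowhere says that failed ratios are dropped. Selection follows only if someone drops them.
- A reader might infer that most infants are affected, because with three single-cytokine denominators the chance that at least one fails is 1 − (1 − q)³ = 49%, 78% or 94%. The protocol defines no such outcome, and each single-cytokine comparison would lose only 20%, 40% or 60%.

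It is also true that no log analysis of cytokines is planned, so the fact that zeros rule one out does not contradict the plan. It matters only for choosing the remedy.

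**Conclusion.** The point holds in limited form. The zero rule, the ratio and the ANOVA are all fixed in the protocol's own text and cannot be carried out together for any sample whose Th2 denominator is undetectable. This is certain algebraically and is not a detail left to an analysis plan.

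The extent is unknown. Over an assumed 20% to 60% of non-detects per cytokine, it runs from about 1% of infants (summed, independent, 20%) to 60% (concordant or single-cytokine, 60%). Whether cohorts would be affected unequally cannot be judged from the protocol.

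The consequences are confined to this immunological outcome and the analyses that use it, including the key comparison at 10.5 months. The change should be made, but the trial's main conclusion does not depend on it.

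**What to change.** 1. State in section D.viii.2.a how the four Th1 and three Th2 cytokines are combined, for example as sums within each group.
2. In section D.xi.2.c, replace 0 with a rule that keeps the ratio computable. One choice is half the detection limit, applied to both numerator and denominator, with the ratio analysed on the log scale and reported as geometric means with confidence intervals.
3. Name the limit for each cytokine from the kit actually used. The 9–15 pg/ml is quoted for a six-cytokine kit without IL-12, and an equivalent kit is allowed.
4. Add a sensitivity analysis by a rank-based method, or by a method that allows for censoring of both numerator and denominator. An ordinary one-sided Tobit model is not enough: a log ratio is left-censored through its numerator, right-censored through its denominator, and unbounded when both are undetectable.
5. Report the share of non-detects by cytokine, cohort and time point.

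The downside is that half the limit gives samples with both parts undetectable a constant set by the assay limits. The sensitivity analysis shows whether that matters. The cost is analysis wording only: no new samples, visits or assays.
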